APPENDIX 6. PARTS B, C, AND D PHARMACOKINETIC TIMEPOINTS

Study Day \pm window in days (Study Week)	Protocol Time	Blood PK (serum)
Day 1	Predose (-1 h)	X
	Dose	
	1 hour (± 5 min)	X
	4 hours (± 30 min)	X
	6 hours (± 30 min)	X
Day 2	24 hours (± 2 h)	X
Day 4 + 1		X
Day 8 \pm 1 (Week 1)		X
Day 11 \pm 1		X
Day 15 \pm 2 (Week 2)		X
Day 29 \pm 2 (Week 4)		X
Day 57 \pm 7 (Week 8)		X
Day 85 \pm 7 (Week 12)		X
Day 113 \pm 7 (Week 16)		X
Day 169 \pm 7 (Week 24)		X
Day 225 \pm 7 (Week 32)		X
Day 281 \pm 7 (Week 40)		X

APPENDIX 7. DOSING SCHEDULE

VIR-3434-1002 Cohort
Dosing Schedule

*The Part B optional cohorts may be dosed at a lower, equivalent, or intermediate dose level relative to the dose levels explored in the planned Part B cohorts, or after cohort 5b at a dose level not exceeding 900 mg.

** Parts C and D may be enrolled after SRC review of available data for all subjects in Part A and Part B through the Week 4 visit for the cohort of subjects in Part B who received a matching or higher dose relative to the proposed starting dose level in Part C and/or D.

APPENDIX 8. ANAPHYLAXIS, CYTOKINE RELEASE SYNDROME, AND IMMUNE COMPLEX DISEASE SUPPORTIVE MEASURES

The following equipment or agents may be needed in the event of a suspected anaphylactic reaction or cytokine release syndrome:

- ECG monitor
- Blood pressure monitor
- Oxygen saturation monitor
- Thermometer
- Tourniquet
- Oxygen
- Mechanical ventilator
- Renal replacement therapy
- IV infusion solutions, tubing, catheters, and tape
- Fresh-frozen plasma and/or cryoprecipitate
- Epinephrine
- Antihistamines, such as diphenhydramine
- Corticosteroids, such as hydrocortisone, prednisolone, and methylprednisolone

The following are procedures that may be followed in the event of a suspected anaphylactic reaction or cytokine release syndrome:

- Maintain an adequate airway
- Stop study drug infusion (if administering by IV infusion and reaction occurs during infusion)
- Call for additional medical assistance
- Apply a tourniquet proximal to the injection site to slow systemic absorption of study drug (if administering by IV infusion and reaction occurs during infusion). Do not obstruct arterial flow in the limb.
- Ensure appropriate monitoring is in place, such as continuous ECG and pulse oximetry monitoring
- Administer epinephrine, antihistamines, corticosteroids or other medications/products as necessary based on the status of the subject and as directed by the physician
- Draw local laboratory samples as appropriate, possibly including evaluation of cytokines

The following equipment or agents that may be needed in the event of suspected immune complex disease:

- Thermometer
- Analgesic and antipyretic agents, such as non-steroidal anti-inflammatory drugs (NSAIDs)
- Antihistamines, such as diphenhydramine
- Corticosteroids, such as prednisone and methylprednisolone
- In extreme cases, equipment for plasmapheresis may be needed

The following are procedures that may be followed in the event of suspected immune complex disease:

- Though unlikely to occur acutely, stop study drug infusion (if administering by IV infusion and reaction occurs during infusion)
- Ensure temperature is appropriately monitored
- Monitor for most common manifestations, including rheumatic (arthralgias) and dermatologic (pruritic rash) findings
- Administer NSAIDs, antihistamines, corticosteroids, or other medications/products as necessary based on the status of the subject and as directed by the physician
- Draw local laboratory samples as appropriate, possibly including complete blood count, erythrocyte sedimentation rate, C-reactive protein, urinalysis, serum chemistry, and evaluation of complement
- In extreme cases, plasmapheresis may be employed

APPENDIX 9. CLINICAL LABORATORY ASSESSMENTS

Hematology	
Complete blood count with differential	
Chemistry	
Albumin	Creatinine clearance
Blood urea nitrogen (BUN)	Gamma glutamyl transferase (GGT)
Calcium	Glucose
Carbon dioxide/bicarbonate	Lactate dehydrogenase (LDH)
Chloride	Potassium
Creatine kinase ^a	Sodium
Creatinine	
Liver Function Tests	
Alkaline phosphatase (ALP)	Aspartate aminotransferase (AST)
Alanine aminotransferase (ALT)	Bilirubin (total and direct)
Coagulation Parameters	
International normalized ratio (INR) time	Prothrombin
Urinalysis	
Bilirubin	Proteins
Glucose	Red blood cells (RBCs)
Ketones	Screen for drugs of abuse
Leukocytes	Specific gravity
Microscopy (if clinically indicated)	Urobilinogen
Nitrite	Visual inspection for appearance and color
pH	
Pregnancy Testing (WOCBP only)	
Beta-human chorionic gonadotropin	Urine pregnancy test
Screening Viral Serology	
Hepatitis B, C ^b , and Delta	Human immunodeficiency virus I and II

^aOnly required if ALT and/or AST is elevated >2x the predose Day 1 baseline value

^bSubjects in Parts B, C, and D with positive HCV screening serology may have HCV RT-PCR performed to determine eligibility

Signature Page for VV-CLIN-000053 v7.0

Approval Task	PPD
---------------	-----

Signature Page for VV-CLIN-000053 v7.0

1. INTRODUCTION

This statistical analysis plan (SAP) for the final analysis is based on the most recent approved clinical study protocol (amendment 4, version 1.0 dated on 20 January 2022), electronic case report form (eCRF), and eCRF completion guidelines (CCG).

This SAP (Methods) documents the planned statistical analyses of safety, pharmacokinetics (PK), and antiviral activity endpoints for the final analysis of study VIR-3434-1002. It may also document analyses for additional antiviral activity variables not specified in the protocol, which will provide supportive information for the scientific understanding of the study intervention entity.

CCI

VIR Biometrics department or a designated contract research organization (CRO) will perform the statistical analysis of the efficacy and safety data. SAS version 9.4 or higher will be used to generate all statistical outputs (tables, figures, listings, and datasets). This SAP will be finalized and approved prior to the final database lock. Any revisions to the approved SAP (Methods) will be documented and approved in an amendment to the SAP.

2. OBJECTIVES AND ENDPOINTS

2.1. Study Objectives

Primary objectives:

- Part A: to evaluate the safety and tolerability of VIR-3434 in healthy adult subjects
- Part B, C, and D: to evaluate the safety and tolerability of VIR-3434 in adult subjects with chronic HBV infection without cirrhosis

Secondary objectives:

- Part A: to characterize the serum PK of VIR-3434 in healthy adult subjects
- Part A: to evaluate the immunogenicity of VIR-3434 (induction of anti-drug antibody [ADA]) in healthy adult subjects
- Part B, C, and D: to characterize the serum PK of VIR-3434 in adult subjects with chronic HBV infection without cirrhosis
- Part B, C, and D: to assess the antiviral activity of VIR-3434 in adult subjects with chronic HBV infection without cirrhosis
- Part B, C, and D: to evaluate the immunogenicity (induction of ADA) of VIR-3434 in adult subjects with chronic HBV infection without cirrhosis

CCI

2.2. Study Endpoints

Primary endpoints (Part A and Part B, C, and D):

- Safety and tolerability assessments determined by treatment-emergent adverse events (TEAEs), serious adverse events (SAEs), clinical laboratory abnormalities, standard 12-lead electrocardiograms (ECGs), vital signs, and physical examination

Secondary endpoints (Part A and Part B, C, and D):

- VIR-3434 serum PK parameters
- Incidence and titers (if applicable) of ADA to VIR-3434
- Maximum reduction of serum HBsAg from baseline
- Maximum change of HBV DNA from baseline (Part D only)

CCI

CCI

[figure not shown]
3. STUDY DESIGN

3.1. Overall Design

VIR-3434-1002 is a Phase 1, randomized, double-blind, placebo-controlled, single ascending dose (SAD) study to evaluate the safety, tolerability, PK, and antiviral activity of VIR-3434 administered by subcutaneous (SC) injection or intravenous (IV) infusion in healthy adult subjects and adult subjects with chronic HBV infection without cirrhosis.

The schema of the study design schema is provided as shown in below Figure 1:

Figure 1: Study Schema

[figure not shown]

Approximately up to 144 participants are planned to be randomized in Part A and Part B, C, and D.

- **Part A:** approximately 8 participants will be randomized (3:1) to either 1 of up to 5 planned dose-sequential cohorts (VIR-3434) or placebo cohort. The healthy participants will be discharged on Day 2 and will be followed up to 24 weeks, as shown in Figure 2.
- **Part B, C, and D:** approximately 8 participants will be randomized (3:1) to either 1 of VIR-3434 dose-sequential cohorts (up to 7/3/3 planned cohorts for Part B/C/D accordingly) or placebo cohort in Part B, C, and D respectively. Participants will be discharged after all study assessments completed on Day 1 and will be followed up to 8 weeks, as shown in Figure 3.

For participants with > 2-fold HBsAg reduction from baseline at Week 8 will be followed for additional 32 weeks up to Week 40 or until the reduction is < 2-fold relative to baseline at 2 consecutive collections, whichever occurs first.

Figure 2: Part A: SAD in healthy adults

* subjects discharge will occur after all assessments are completed on Day 2

Figure 3: Parts B, C, and D: SAD for adults with chronic HBV infection without cirrhosis

The dose escalation of study intervention and the corresponding cohorts with the enrollment status for Part A and Part B, C, and D are showed in below Table 1 and Table 2 respectively:

Table 1: Dose Escalation Cohorts in Part A

Study Part	Cohort	Route	Dose Level (VIR-3434)	Enrolled
A	1a	SC	90 mg	Yes
A	2a	SC	300 mg	Yes
A	3a	SC	900 mg	Yes
A	4a (optional)	IV	900 mg	Yes
A	5a (optional)	IV	3,000 mg	Yes

Table 2: Dose Escalation Cohorts in Part B, C, and D

Study Part	Cohort	Route	Dose Level (VIR-3434)	Enrolled
B	1b	SC	6 mg	Yes
B	2b	SC	18 mg	Yes
B	3b	SC	75 mg	Yes
B	4b	SC	300 mg	Yes
B	5b	SC	up to 900 mg	No
B	6b (optional)	SC	up to 900 mg	No

Study Part	Cohort	Route	Dose Level (VIR-3434)	Enrolled
B	7b (optional)	SC	up to 900 mg	No
C	1c (optional)	SC	18 mg	Yes
C	2c (optional)	SC	75 mg	Yes
C	3c (optional)	SC	300 mg	Yes
D	1d (optional)	SC	75 mg	Yes
D	2d (optional)	SC	300 mg	Yes
D	3d (optional)	SC	up to 900 mg	No

3.2. Sample Size

The sample size is based on practical consideration, and no formal sample size calculation was performed.

3.3. Randomization

For Part A, in each cohort, 2 sentinel subjects will be randomized 1:1 to receive VIR-3434 or placebo. These subjects will be dosed and monitored for at least 24 hours in an inpatient setting; if the investigator has no safety concerns, the remainder of the subjects in the same cohort will be randomized 5:1 to receive VIR-3434 or placebo.

For Part B, C, and D, in each cohort, 2 sentinel subjects will be randomized 1:1 to receive VIR-3434 or placebo by SC injection. These subjects will be dosed and monitored through at least 72 hours post dose; if the investigator(s) have no safety concerns, the remainder of the subjects in the same cohort will be randomized 5:1 to receive VIR 3434 or placebo by SC injection.

An Interactive Web Response System (IWRS) will be used to assign participants to treatment group. The randomization list will be produced by VIR Biometrics or a qualified randomization vendor.

3.4. Blinding and Unblinding

This is a double-blinded study. Investigators, designated study staff, and participants are blinded to treatment allocation. The Sponsor is not blinded.

An individual cohort will be unblinded when all subjects enrolled in the cohort complete the Week 8 visit. The Sponsor will communicate treatment assignments to investigators, and investigators will share treatment assignment with the subject. Please refer to the VIR-3434-1002 Blinding Plan for more details.

3.5. Planned Analysis

The final analysis will be conducted when all participants have completed or prematurely discontinued the study and the data have been cleaned, finalized, and locked.

4. STATISTICAL HYPOTHESES

There are no formal statistical hypotheses planned for this study.

This study is exploratory in nature. No multiplicity adjustment will be made.

5. ANALYSIS SETS

5.1. All-Randomized Set

The All-Randomized Set includes all participants who were randomized in the study. This analysis set will be used for individual participant data listings and disposition data summary tables, unless otherwise specified.

5.2. Full Analysis Set

The Full Analysis Set (FAS) includes all randomized participants who received at least 1 dose of study drug. The FAS will be used to summarize participant demographics and baseline characteristics, and analysis for antiviral activity endpoints, unless otherwise specified.

5.3. Safety Analysis Set

The Safety Analysis Set includes all participants who received at least 1 dose of study drug. The Safety Analysis Set will be used for all safety analyses.

5.4. PK Analysis Set

The PK Analysis Set includes all participants in the FAS with at least 1 measurable postdose concentration data to provide interpretable results. The PK Analysis Set will be used for all PK analyses.

5.5. Immunogenicity Analysis Set

The Immunogenicity Analysis Set includes all participants in the FAS who had at least 1 sample that has undergone testing for immunogenicity, including screening, titer, or neutralizing characterization, as applicable. The Immunogenicity Analysis Set will be used for analyses of the immunogenicity endpoints.

6. STATISTICAL ANALYSES

6.1. General Considerations

The study assessments and time points schedule are provided in the study protocol. All individual participant data for those who were randomized to study intervention will be presented in data listings.

Continuous variables will be summarized using the following descriptive summary statistics: the number of participants (n), mean, standard deviation (SD), median, minimum value (min), and maximum value (max), unless otherwise specified.

In general, the precision of the measurement for each continuous variable will be used to determine the number of decimal places to present in tables, figures, and derived listings. Unless otherwise specified, raw data will be presented with the same number of decimals as collected, and derived data will be presented with an appropriate number of decimals based on general practice, mathematical rationale, or scientific rationale. Any values that require transformation to standard units (metric or SI) will be converted with the appropriate corresponding precision.

Categorical variables will be summarized using counts and percentages. Generally, percentages will be presented to 1 decimal place.

Baseline Value: Unless otherwise specified, the baseline value will be defined as the most recent non-missing (scheduled or unscheduled) measurement collected prior to the administration of study intervention.

If multiple measurements that are prior to dosing are recorded on the same date and with the same time or if time is not available, then the average of these measurements will be considered the baseline value.

Absolute change from baseline will be calculated as post-baseline value - baseline value.

Treatment-emergent (TE) period: Unless otherwise specified, the TE period will include the time from the administration of study drug until the Week 24 visit (or the Day 169, if the Week 24 visit is unavailable) for Part A, and the Week 8 visit (or the Day 57, if the Week 8 visit is unavailable) for Part B, C, and D.

Unscheduled visits: Unscheduled visit measurements will be included in analysis as follows:

1. In scheduled visit windows per specified visit windowing rules, if applicable
2. In the derivation of baseline and last follow-up measurements
3. In the derivation of maximum and minimum values and/or maximum and minimum change from baseline values during follow-up period or TE period
4. In individual participant data listings as appropriate

Visit Windows: The analysis visit windowing rules for protocol-defined visits are provided in Appendix 2.

Incomplete/Missing data: In general, missing data will not be imputed, unless specified otherwise.

For virology tests and safety laboratory parameters, the following rules will be applied in calculation of summary statistics and absolute change from baseline values:

- If a data point is missing by reported as “< lower limit of quantification (LLOQ) or < limit of detection (LOD)” with “Target Not Detected (TND)” or reported as the meaning of “Not Detected”, then the missing data point will be imputed as zero.
- If a data point is missing by reported as “< LLOQ or < LOD” with “Target Detected (TD)”, then the missing data point will be imputed as the half of LLOQ value or 1 unit less than the LOD value, respectively. For example, if the LOD values are 0.5 and 0.03, then the imputed values will be 0.4 and 0.02. When the LOD value is 1, it will be imputed as 0.9.

- If a data point is missing by reported as “< LLOQ or < LOD” without knowing “TD or TND”, then the missing data point will be treated as “< LLOQ, TD or < LOD, TND”.
- If a data point is missing by reported as “> upper limit of quantification (ULOQ)” without knowing “ULOQ”, then the missing data point will be imputed as 1 unit greater than the value of ULOQ.
- If a data point is missing by reported as the meaning of “no results obtained”, then it is considered as the missing data and not included in data summary and analysis.

Logarithm transformation will be used for analysis of virological variables. For the \log_{10} transformed data using LOD value, 1) a missing data point due to untransformed value of zero will be imputed as zero, when $\text{LOD} > 1$; and 2) a missing data point due to untransformed value of zero will be imputed as \log_{10} (1 unit less than LOD value), when $\text{LOD} < 1$.

The reported value will be used in individual subject listings for all virology tests and safety laboratory parameters.

Outliers: No formal statistical analyses will be performed to detect and/or remedy the presence of statistical outliers.

Repeated Observations: Measurements recorded at different time points are defined as repeated observations. If an assessment has planned repeated measurements, then statistical summaries will present all planned time points, as appropriate.

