4.2. Parts B, C, and D Endpoints

The primary endpoints are as follows:

- Number of subjects with TEAEs and SAEs
- Number of subjects with clinical laboratory abnormalities

The secondary endpoints are as follows:

- VIR-3434 serum PK parameters, for example: C_{max} , C_{last} , T_{max} , T_{last} , AUC_{inf} , AUC_{last} , $\%AUC_{exp}$, $t_{1/2}$, λ_z , V_z/F , and CL/F.
- Incidence and titers (if applicable) of ADA to VIR-3434
- Maximum reduction of serum HBsAg from baseline (Day 1 predose)
- Part D only: maximum change of HBV DNA from baseline (Day 1 predose)

CCI

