9.2.2. Assessment of Severity

Standard toxicity grading according to the CTCAE (V5.0) will be used to grade AEs and laboratory abnormalities. Definitions of severity per CTCAE (V5.0) are presented in Table 8.

Table 8: CTCAE (V5.0) Definitions of Severity

Severity	Definition
Grade 1	Mild; asymptomatic or mild symptoms; clinical or diagnostic observations only; intervention not indicated.
Grade 2	Moderate; minimal, local or noninvasive intervention indicated; limiting age-appropriate instrumental ADL. Instrumental ADL refer to preparing meals, shopping for groceries or clothes, using the telephone, managing money, etc.
Grade 3	Severe or medically significant but not immediately life-threatening; hospitalization or prolongation of hospitalization indicated; disabling; limiting self-care ADL. Self-care ADL refer to bathing, dressing and undressing, feeding self, using the toilet, taking medications, and not bedridden.
Grade 4	Life-threatening consequences; urgent intervention indicated.
Grade 5	Death related to AE.

ADL = activities of daily living

Source: [NCI 2017](#)

9.3. Investigator Requirements and Instructions for Reporting Adverse Events and Serious Adverse Events to Vir

AEs

After informed consent, but prior to initiation of study medication, the following types of events should be reported: AEs related to protocol-mandated procedures and all SAEs.

Following initiation of study drug, collect all AEs, regardless of cause or relationship, through the required follow-up period (through Week 24 for Part A and through Week 8 for Parts B, C, and D).

Following Week 8 in Parts B, C, and D, all SAEs and targeted AEs related to immune reactions, immune complex disease (eg, vasculitis, glomerulonephritis, serum sickness and serum sickness-like reactions, extra-hepatic manifestations of HBV), new onset hepatic disorders (eg, hepatic decompensation, hepatic necrosis), and new onset chronic diseases requiring ongoing medical management should be collected through the end of extended follow-up.

[figure not shown]
SAEs

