10.4. Safety Analysis

All safety analyses will be performed using the Safety Analysis Set.

If applicable, safety will be evaluated by assessment of clinical laboratory tests, physical examinations, ECGs, vital signs measurements at various time points during the study, and by the documentation of AEs.

All safety data collected on or after study drug administration up to the last scheduled visit, unless specified otherwise, will be summarized by cohort for each VIR-3434 dose and placebo.

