10.4.2. Laboratory Evaluations

Selected laboratory data will be summarized (n, mean, SD, median, Q1, Q3, minimum, and maximum) by cohort and study visit along with corresponding change from baseline. Graded laboratory abnormalities will be defined using CTCAE Version 5.0 grading scale.

The incidence of treatment-emergent laboratory abnormalities, defined as values that increase at least 1 toxicity grade from baseline at any postbaseline timepoint will be summarized by treatment group. If the relevant baseline laboratory data are missing, then any abnormality of at least Grade 1 will be considered as treatment-emergent.

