6.4. Safety Analyses

Safety analyses will be based on data from the TE Period for all participants in the Safety Analysis Set, unless otherwise specified. All safety data will be included in the individual participant listings. Participants will be analyzed according to the treatment dose level they received.

The overall safety profile of the study intervention will be assessed in terms of the following safety and tolerability assessments:

- TEAEs
- Clinical laboratory
- ECG
- Vital signs
- Physical examination

Only descriptive analysis of safety will be performed, and no statistical testing will be performed.

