6.4.2. Clinical Laboratory

Clinical laboratory data collected (through central laboratories only, unless otherwise specified) will be analyzed using both quantitative and qualitative methods and presented by VIR-3434 treatment cohort and placebo, for each of Part A, B, C, and D. The analysis will be based on values reported in conventional units.

For the treatment-emergent laboratory measurements, the observed values and change from baseline values of the continuous hematology, serum chemistry, and coagulation results will be summarized descriptively (n, mean, SD, median, min, max) at each visit.

For ALT, AST, total bilirubin, lymphocytes, neutrophils, platelets, and INR, mean (\pm SD) of the observed values will be plotted by visit and by each VIR-3434 treatment cohort and placebo for each of Part A, B, C, and D.

The Common Terminology Criteria for Adverse Events (CTCAE, v5.0) will be used as the reference on grading scale to assign severity (toxicity) grades (1 to 4) to abnormal results for the laboratory of interest as shown in Appendix 5. Grade 0 refers to the normal values that do not meet the criteria of laboratory abnormalities.

For treatment-emergent laboratory abnormalities, the number and percentage of participants who met at least 1 threshold criterion of severity grade will be summarized by VIR-3434 treatment cohort and placebo for each of Part A, B, C, and D, based on the most severe postdose abnormality grade during TE period for a given laboratory test. The threshold of severity grade shifted from baseline will also be summarized for selected laboratory tests.

In addition, a separate listing containing individual participants with hematology, chemistry, coagulation, and urinalysis values will be provided based on the Safety Analysis Set by subject ID and visit in chronological order including data collected from both scheduled and unscheduled visits. Values falling out of the relevant normal range (between the value of LLN and ULN) or having the severity grade of 1 or higher on laboratory abnormalities will be flagged as appropriate.

Results of positive urine/serum pregnancy test will be listed in an individual participant data listing only.

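### For Parts B–D the SAP's visible safety and antiviral tables stop at Week 8, although SAEs, liver tests and HBsAg are collected to Week 40

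*SAP*

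**What the plan says.** **Protocol.** For Parts B–D, section 4.2 lists as primary endpoints "Number of subjects with TEAEs and SAEs" and the number of subjects with laboratory abnormalities. A secondary endpoint is "Maximum reduction of serum HBsAg from baseline (Day 1 predose"), and Part D adds the maximum change in HBV DNA. None has a time limit. Section 10.4 says that "All safety data collected on or after study drug administration up to the last scheduled visit, unless specified otherwise" will be summarized by cohort. Section 10.4.2 defines a treatment-emergent laboratory abnormality by "values that increase at least 1 toxicity grade from baseline at any postbaseline timepoint". Under section 9.3, SAEs and a targeted set of AEs arising after Week 8 "should be collected through the end of extended follow-up". Appendix 3 schedules liver tests, chemistry and HBsAg at Weeks 12, 16, 24, 32 and 40 for subjects in extended follow-up.

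**SAP.** Section 6.1 closes the TE period at Week 24 for Part A "and the Week 8 visit (or the Day 57, if the Week 8 visit is unavailable) for Part B, C, and D". Section 6.4 states: "Safety analyses will be based on data from the TE Period for all participants in the Safety Analysis Set", unless otherwise specified. The AE tables in 6.4.1 cover TEAEs and serious TEAEs; AEs after the TE period are a defined class that appears only in listings. The graded laboratory table in 6.4.2 is "based on the most severe postdose abnormality grade during TE period for a given laboratory test". Sections 6.7.1 and 6.7.2 limit the HBsAg nadir, the Part D HBV DNA nadir and HBsAg loss to Week 8. Section 6.8.1 declares the changed TEAE definition and gives a consistent reporting period as the reason. It does not mention a changed laboratory definition or a Week 8 limit on nadir or HBsAg loss.

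**The concern.** The endpoints are open-ended and the data run to Week 40, but the tables that report them close at Week 8. Followed exactly, the SAP leaves a post-Week 8 SAE or ALT grade shift out of the primary-endpoint counts. It also understates maximum HBsAg reduction, read as the protocol words it, for any subject whose nadir comes later. Those still under observation after Week 8 are the HBsAg responders, for whom maximum reduction matters most. The protocol itself names immune complex disease and new hepatic disorders as events to collect in this period.

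The SAP also does not fit its own text. Section 2.2 restates SAEs separately from TEAEs, and maximum HBsAg reduction, again without a time limit. Appendix 2 defines extended-follow-up windows for liver tests, chemistry and HBsAg and says analysis visit names serve tables and figures, yet no visible safety or antiviral table uses these windows.

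**Working it through.** No power or sample-size figure is involved; both documents say no formal calculation was done. The check compares the texts and counts from the visit schedule.

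**1. Side by side, Parts B–D**

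| Item | Protocol limit | Collected after Week 8 | Visible SAP table |
|---|---|---|---|
| SAEs | none (4.2, 10.4) | yes (9.3) | serious TEAEs to Week 8; later SAEs listed |
| Targeted AEs | none (10.4.1) | yes (9.3) | TEAEs to Week 8; later AEs listed |
| Liver-test and chemistry grades | any postbaseline time (10.4.2) | yes, 5 visits | worst grade to Week 8; later values listed |
| Maximum HBsAg reduction | none (4.2) | yes, 5 visits | nadir to Week 8 |
| HBsAg loss | none (10.6) | yes | both results by Week 8 |

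Hematology and coagulation are not scheduled after Week 8, so the laboratory gap concerns liver tests and chemistry. HBsAg loss is an analysis in protocol 10.6, not a visible secondary endpoint. PK, disposition and ADA-type summaries are not capped and are not at issue.

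**2. Follow-up time.** 8 + 32 = 40 weeks, as the SAP states. For a subject who completes it, Day 57 to Day 281 is 224 of 280 post-dose days, or 32/40 = 80%.

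**3. Scheduled post-dose visits (protocol Appendix 3).**
- Liver tests: Days 2, 4, 8, 15, 29, 57 (6) plus 5 extended = 11; 5/11 = 45% fall outside.
- HBsAg: the same six plus Day 11 (7) plus 5 extended = 12; 5/12 = 42% fall outside.

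**4. Confirmation of HBsAg loss.** Two results at least 2 weeks apart are needed. If loss is first seen at Day 57, the next scheduled sample is Day 85, 28 days later. That satisfies the spacing but lies beyond the SAP's limit, so such a loss cannot be confirmed on scheduled visits.

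**5. Group sizes.** SAP Table 2 shows 4 (B) + 3 (C) + 2 (D) = 9 enrolled cohorts. At the planned 6:2, that is 9 × 6 = 54 active and 9 × 2 = 18 placebo. One late SAE would move a cohort from 0/6 to 1/6, or 16.7 percentage points.

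**6. Share of SAE-collection time after Week 8.** The fraction f entering extended follow-up is not given. If all who enter stay to Week 40 (an upper bound, since follow-up can stop early), the share is 32f/(8 + 32f):
- f = 0.10: 3.2/11.2 = 29%
- f = 0.25: 8/16 = 50%
- f = 0.75: 24/32 = 75%

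These fractions are assumptions. The results are shares of observation time, not estimates of bias.

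**7. Context.** Protocol 2.3.2 predicts a half-life of about 58 days. Its parameters reproduce this: k10 = 0.0657/2.43 = 0.0270, k12 = 0.6127/2.43 = 0.2521, k21 = 0.6127/2.85 = 0.2150 per day. The slow rate is [0.4942 − √(0.4942² − 4 × 0.0270 × 0.2150)]/2 ≈ 0.0121, giving ln 2/0.0121 ≈ 57.5 days before rounding. About 0.5^(56/58) = 51% of the terminal-phase level would remain at Day 56. This assumes linear PK without target binding. It does not show that any nadir or event falls after Week 8.

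**The case against.** The case for Week 8 is a reasonable one. The AE part is declared and reasoned in SAP 6.8.1, whose row cites all of section 6.4. Protocol 10.4 allows exceptions, and Week 8 is the protocol's own end of required follow-up. Nothing is lost: all AEs are listed, SAEs and deaths carry a TEAE flag, laboratory values are listed with grade flags, and the number entering extended follow-up is tabulated. Later data come only from responders, who would have up to five times the observation of others (40/8). A maximum over 12 HBsAg results can only equal or exceed one over 7, so a Week 40 maximum is not comparable with placebo. The protocol sets no horizon for that maximum, so the SAP may be read as filling a gap. Parts of the SAP are redacted and may use the extended windows.

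Much of this stands. For AEs it is a reporting gap in a declared change, the Week 8 tables are the right controlled comparison, and the point is limited to visible text. The mean plots of ALT, AST and bilirubin state no end visit, but the TE default applies and means do not count abnormalities. The protocol also ties its 4-week safety review to the expected timing of immune complex disease and hepatotoxicity, which suggests that late events may be few.

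It does not answer the rest. The 6.8.1 row is worded for TEAEs, so it does not expressly change the any-timepoint rule in protocol 10.4.2. The exception in 10.4 does not reach that rule or the HBsAg and HBV DNA endpoints. Listings do not replace counts for a primary endpoint defined as a number of subjects.

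**Conclusion.** The concern holds. In the visible SAP, the Parts B–D safety and antiviral tables end at about Week 8 (the Week 8 analysis window extends slightly past Day 57), while the endpoints have no such limit and the data run to Week 40. The laboratory, nadir and HBsAg-loss limits are not declared as changes to the protocol.

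The measurable size is structural: up to 80% of follow-up time and 42–45% of the relevant visits for a subject who reaches Week 40. The effect on results is unknown, because the documents give neither the number entering extended follow-up nor the timing of any nadir or event. The change is worth making before database lock, but the Week 8 analyses themselves remain valid.

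**What to change.** Keep the Week 8 tables as the placebo-controlled comparison and add, for Parts B–D by cohort:

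- Subjects with any SAE, any targeted AE, and any liver-test or chemistry grade increase from baseline at any postbaseline time, through end of study. Show the number entering extended follow-up as a second denominator.
- Maximum HBsAg reduction and HBsAg loss over all visits to Week 40, beside the Week 8 results, with Week 12 allowed to confirm loss first seen at Week 8.
- For Part D, Week 40 HBsAg and HBV DNA results derived from values before any NRTI or interferon start, since protocol 7.5.2 permits such starts after Week 8. Because 7.5.2 also permits urgent starts earlier, the SAP should state how those values are handled.
- Entries in SAP 6.8.1 declaring the Week 8 limits on laboratory grades, nadir and HBsAg loss.

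The cost is a few descriptive tables from data already collected and, for laboratory and HBsAg results, already windowed in Appendix 2. The drawback is interpretive: after Week 8 the subjects are selected by response, largely without placebo controls, may stop early, and have narrower AE collection. The tables must be labelled accordingly and not read as a comparison with placebo.
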